## **Trial Summary**

Title	Support, Positioning and Organ Stabilisation during Breast Cancer Radiation Therapy: The SuPPORT 4 All bra.
Aim	
 
This feasibility trial is an essential preliminary to a definitive Randomised
 
Controlled Trial (RCT). The purpose of this feasibility trial is to ensure the design and methods of that future trial are sound, practicable and feasible. The aims of the feasibility trial are:
 
1. To test the feasibility, practicality, and acceptability of the study design and protocol;
 
2. To resolve practical issues for the conduct of the future RCT such as the reproducibility of the outcome measures, and recruitment and attrition rates;
 
3. To investigate the acceptability of the care pathway to patients and Clinicians and to refine it prior to the full RCT;
 
4. To inform the sample size calculation for the full trial.
 

Eligibility Criteria	All of the following criteria need to be met for inclusion in the study:
	
 
Age ≥18 years
 
Have undergone conservative surgery leaving an intact breast.
 
Invasive carcinoma of the breast
 
pT1-3, pN0-1, M0 disease
 
Referred for whole breast radiotherapy only
 
Able to give written informed consent.
 
A bra cup size that fits in the S4A bra size 3 and above (ie 28F/30E/32DD/34D/36C and above).
 
 All standard systemic therapies are allowed except those prescribed concurrent chemotherapy.
	
 
Exclusion Criteria
 
Previous ipsilateral or contralateral breast cancer (including DCIS).
 
Concurrent cytotoxic chemotherapy, (sequential adjuvant chemotherapy is allowed).
 
Radiotherapy to regional lymph nodes.
 
Requires a radiotherapy boost to the site of the primary tumour bed.
 

Study Design	This is a prospective randomised feasibility trial.
Endpoints	Primary feasibility endpoint Recruitment of 50 participants recruited in a 6-month recruitment window at 1 centre

	Secondary feasibility endpoints	
	
 
Recruitment and attrition rates (CONSORT data): number of patients assessed for eligibility; reasons for exclusion, numbers discontinuing intervention (with reasons), numbers analysed and excluded from the analysis.
 
Number of missing values/incomplete cases: Acceptable rates of missing values for all the questionnaires prospectively defined as 0.5% in line with industry standards for phase I-III clinical trials.
 
Intervention adherence: Defined objectively as the number of radiotherapy fractions where the bra is used (for the intervention group) divided by the number of fractions prescribed.
 
Ease of radiation planning using the bra and ease (or difficulty) of producing an acceptable plan using the bra compared with no bra.
 
Intervention fidelity: During the study period site observations will be undertaken of treatment set-up for patients in both the control and intervention arms to ensure the support bra is used and positioned correctly and technique protocols are used in a standard manner across intervention and control groups. A checklist of criteria that reflects the protocol for using the support bra will be used to monitor intervention fidelity.
 
Feasibility of recruiting future participating centres.
 
Decision on primary endpoint for main trial.
 
	
	Primary Efficacy Endpoint Treatment accuracy and reproducibility will be collected as part of this feasibility trial. We would expect the S4A bra to either maintain or improve on existing levels of accuracy (where approximately 73.3% of cases had mean systematic errors <3mm and approximately 75% of cases had mean random errors <3mm for central lung depth on treatment verification images. Results will be viewed in relation to improvements in the dose to organs at risk (mean lung and mean heart dose where applicable).	
	
 
Secondary efficacy Endpoints
 
Skin reactions.
 
Dose to organs at risk.
 
Breast oedema.
 
Patient comfort.
 
Patient modesty.
 
Patient empowerment.
 
Participant views on acceptability of the intervention.
 
Therapist views on the acceptability of the intervention.
 
Body Image.
 
	
Sample Size	A sample size of 40 patients allows a standard deviation, for a continuous outcome such as accuracy of radiotherapy (measured in mm), to be estimated to within a precision of approximately ±23% of its true underlying value with 95% confidence. Therefore, allowing for a 20% attrition or loss to follow-up we propose to recruit and randomise 25 patients per group (50 in total). This SD estimate will be synthesised with standard deviations observed in other published studies and on going trials to provide a robust estimate for use in the sample size calculation for the full trial.	

Outcomes	Random and systematic treatment errors, using on-treatment portal
	images.
	• Skin reactions using the Radiation Therapy and Oncology Group skin
	scoring assessment (RTOG)(1) both staff scored and patient self –
	reported using a new lay reporting skin assessment tool (developed
	jointly by our patient group and health care practitioner group).
	Dose to organs at risk, including mean ipsilateral lung dose, combined
	total lung dose, and mean heart dose (for those treated for a left breast cancer).
	• Incidence of dry/moist desquamation in the inframammary fold.
	• Breast oedema measured via a new self reporting tool (SELF- SizE, Look,
	Feel, tool).
	Patient comfort measured by a new comfort questionnaire developed
	from interviews with healthy volunteers that have tried the support bra
	
 
Patient modesty and experience measured by a storyboard incorporating questions from the patient modesty scale(2).
 

	• Patient empowerment using the 15-item patient empowerment scale for cancer patients(3)
	• Participant views on acceptability of the intervention using a specially designed Technology Acceptance questionnaire based on the Technology Acceptance Model(4).
	Therapist views on the intervention using a specially designed
	Technology Acceptance questionnaire(4).
	• Body Image using the 10-item body image scale(5)

## 1.0 Background

Breast cancer affects a substantial proportion of the population(6); with over 1.67 million women diagnosed globally in 2012(7). For many of these women the primary treatment is local excision (LE) followed by external beam radiotherapy to the whole breast. Traditionally this has been given using basic tangential radiotherapy beams. New technology employing complex approaches such as 3D conformal and Intensity Modulated Radiotherapy (IMRT) provide the opportunity to spare sensitive structures that lie close to the breast; these require greater accuracy in patient alignment. Set up inaccuracies (anterior-posterior and superior-inferior systematic displacements) have dosimetric consequences that vary depending on breast gradient, standard or IMRT based techniques and magnitude of error(8) and may increase the risk of a loco-regional recurrence(9) or a poorer cosmetic outcome (10). Added to this in the majority of radiotherapy centres worldwide women lie for breast irradiation, bare from the waist upwards, with up to four therapy radiographers (including men) adjusting and manipulating their thorax and breast in preparation for treatment. Most radiotherapy centres rely on the use of permanent tattoos marked on the patient and laser systems aligned to the machine. However, accuracy using this approach can be problematic(11) and the use of permanent tattoos is of concern to many patients(12). In addition, women with large (above a D bra cup size) or pendulous breasts can be difficult to position. Specifically, overhang of the breast inferiorly produces a self-bolusing effect that leads to an increased skin dose in the lower part of the breast and on the chest wall underneath the tissue overhang. The use of a support bra would lift the breast tissue away from the chest wall, reduce the skin reaction at the inferior aspect, making the potential cosmetic outcome and treatment experience for women with larger breasts more comparable to that experienced by women with smaller breasts

Currently no immobilisation device is available for use with supine positioning that can accurately stabilise the breast while also maintaining patient dignity(13). We have developed a support bra and determined proof of concept of the design through experimental testing.

#### 2.1.Why is this research important -

Survival rates following LE and radiotherapy are good (79-98% at 4-5 years). With local recurrence generally low (0.3-10%)(14-18) more women are living with the side effects of therapy with survival projected to reach 1.7 million by 2040(19).

The long-term effects of incidental cardiac irradiation during breast radiotherapy are a concern. First highlighted in the Early Breast Cancer Trialists Collaborative Group (EBCTCG)(20) report in 1995, more recent studies have indicated that while modern radiotherapy techniques do not increase mortality from cardiac irradiation, the impact of cardiac morbidity on breast cancer survivors is a worry(21). Review of doses received by the heart in patients treated between 1958 and 2001 in Sweden and Denmark(22, 23) indicated a 7.4% increase in the rate of major coronary events for each increase of 1Gray (Gy) in the mean radiation dose delivered to the heart (95% CI, 2.9 to 14.5, p<0.001). In order to reduce the dose to the heart many centres are employing cardiac avoidance techniques including voluntary deep inspiration breath hold (vDIBH)(24) which has been shown to reduce mean heart dose by approximately 50%(24). However, using vDIBH techniques adds further opportunity for patient movement during the beam on time and requires imaging (adding additional radiation dose to the patient) to ensure accuracy especially in the caudo-cephalic direction where mean systematic error in heart position of 0.5cm have been

## reported(25).

In our early testing of the first prototype we were able to demonstrate that using the support bra on a large breast phantom reduced the mean heart dose from 5.1Gy (no bra) to 3.7Gy (with the prototype support bra) p=0.036. Thus allowing the opportunity to reduce long-term sequela that require costly interventions and reduce patient quality of life.

Additionally, clinical trials are testing partial organ techniques compared with whole breast irradiation (eg IMPORT low trial) in cases where there is low risk of tumour recurrence. The principle is to spare sensitive tissues by reducing the volume of breast tissue irradiated (26) but partial organ techniques require accurate positioning if favourable cosmetic outcomes and local control are to be achieved(10). Interim data from some Phase III partial breast clinical trials raised concerns over lower than anticipated cosmetic outcomes(27, 28). It is possible this was influenced by poor breast stabilisation. Many centres are employing image-guided radiotherapy (IGRT) as a way of confirming radiotherapy field placement prior to treatment exposure. IGRT incorporates kilovoltage imaging on the treatment set, this additional imaging increases the total body dose of radiation received by the patient, for younger women there is concern that the life time additional risk from this extra exposure to the contra-lateral breast could increase the likelihood of a second cancer(29). If there was greater confidence in the immobilisation method used to stabilise the breast this could reduce the frequency of on-treatment imaging.

Our support bra has the potential to stabilise the breast (increasing treatment accuracy) and reduce the dose to organs at risk such as the heart (for women treated for a left breast tumour) while providing modesty during treatment delivery.

## **3.0 Study Aim and Research Questions.**

This feasibility trial is an essential preliminary to a definitive Randomised Controlled Trial (RCT). The aim of the definitive RCT is to assess the effectiveness and cost-effectiveness of a support bra for immobilising breast tissue during breast irradiation for women that have been diagnosed with breast cancer (and have undergone removal of the tumour leaving an intact breast i.e have undergone conservative surgery) compared to current practice of no immobilisation. The purpose of this feasibility trial is to ensure the design and methods of that future trial are sound, practicable and feasible. The aims of the feasibility trial are:

1. To test the feasibility, practicality, and acceptability of the study design and protocol;

2. To resolve practical issues for the conduct of the future RCT such as the reproducibility of the outcome measures, and recruitment and attrition rates;

3. To investigate the acceptability of the care pathway to patients and Clinicians and to refine it prior to the full RCT;

4. To inform the sample size calculation for the full trial.

This feasibility trial proposes to answer the following research questions in relation to the prototype support bra:

## Research questions-bra functionality

- Is the design and current functionality of the bra able to fit with current set-up procedures without too much process adaptation?
- Does the inflation bladder retain consistency across the treatment course?

## Research questions-bra accuracy

• What are the random and systematic errors in breast positioning with the immobilisation support bra compared with a control group with standard immobilisation (no bra)? (specifically the proportion of set ups achieved with ≤3mm set-up error(30))

• Is accuracy of positioning using the support bra the same across all breast sizes?

Research questions- Improvements in care

- What are the differences in the dose to organs at risk when the support bra is used compared with no support bra?
- Does the support bra reduce the incidence of moist desquamation in the inframmary fold (grade 2 using the Radiation Therapy Oncology Group acute morbidity scoring system)?(30)

Research questions-patient experience

- Is the current inflation bra design appropriate for patients' aesthetic, and comfort needs?
- Does the support bra provide measureable changes in patient modesty? and
- Does the support bra allow measurable changes in feelings of empowerment compared with the standard no immobilisation process?

Research questions- Health Economics

• Are there any treatment related cost savings from using the support bra?

The primary endpoint is a support bra that is technically acceptable to health-care professionals (HCPs) and aesthetically acceptable to patients.

## 3.1. Success or stop go criteria for this feasibility trial

## Table 1 Stop/Go Criteria for the Feasibility Trial.

Criteria to be assessed and potential outcome	Proposed Action at end of feasibility trial
Random and systematic errors > 3mm for CLD in more than 30% of cases using the bra.	Review bra fit comments across sample and review training and bra use instructions. Further experimental testing (use of healthy volunteers and 3D surface imaging to measure improvements in accuracy and reproducibility, recommended before definitive RCT.
Mean lung dose, no improvement in mean lung doses over control arm.	Review inflation levels used in the study and recommend changes to inflation levels used, further experimental testing recommended before definitive RCT.
Mean heart dose (left sided cases only), no improvement in mean heart doses over control arm.	Review inflation levels used in the study and recommend changes to inflation levels used, further experimental testing recommended before definitive RCT.
Recruitment to sample size (n=50) takes longer than 6-months.	Review recruitment process and devise strategy to enhance recruitment to the definitive RCT.

Retention in study < 80%	Review attrition reasons and identify strategies to remedy ahead of full RCT.
Intervention adherence < 84%	Review comfort questionnaire responses and consider strategies to enhance patient comfort.
RTOG score in the intervention arm ≥3 in one or more cases.	Review of bra fit, inflation levels and dosimetry for affected cases, recommend bra refinement. If a grade 3 (or above) reaction occurs during the course of radiotherapy, treatment will be reviewed by the patient's Oncologist immediately. Treatment may continue without the bra following re-planning at the discretion of the treating Oncologist

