#### 4.0 Trial Design

The SuPPORT 4 All (S4A) study is a single centre randomised feasibility trial. The safety of the product in terms of the radiation absorption properties have been fully tested through a series of physics tests performed on both a 6 and 10MV linear accelerators (see Appendix 1). The positional accuracy achievable using the S4A bra has been tested through a Healthy Volunteer Study using 3D surface scanning (stereophotogrammetry). Hence the purpose of this feasibility trial is to test the acceptability of the SuPPORT 4 All bra by patients (in terms of comfort, modesty and usability) and staff (in terms of ease of daily set-up) and to assess the appropriateness of a range of measurement tools that might be used in post implementation surveillance as part of the on-going update to the product technical file.

This study also proposes to assess the impact of the bra on the ability or ease of producing an acceptable radiation treatment plan. To achieve this those patients randomised to the intervention arm will undergo two planning CT scans (using a repeated measures design); one CT scan while

wearing the S4A bra and one scan as normal without the bra. Thus enabling a direct comparison between participants of dose homogeneity achievable with and without the bra.

The following parameters are standard tools or measures that will be adopted in the study (see section 7.0 for more details) some are validated tools others are being tested for the first time in this study:

- Skin reactions using a standard measuring tool Radiation Therapy and Oncology Group skin scoring assessment (RTOG)(1).
- Incidence of moist desquamation in the inframammary fold.
- Dose to organs at risk (mean lung and mean heart doses) taken from the patient's individual dosimetry plan (see section 7 for further details).
- Patient comfort measured via a new comfort questionnaires designed specifically for this study.
- Patient modesty measured by aspects of the patient modesty scale(2) within a newly developed story board of the radiotherapy journey to measure patient experiences.
- Patient empowerment using the 15-item patient empowerment scale for cancer patients(32)
- Technology acceptance from both healthcare practitioners and patients using an adapted Technology Acceptance Tool (based on the Technology Acceptance Model(4)).
- Body Image using the 10-item body image scale(5)

[figure not shown]

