#### 5.2. Number of patients

The sample size for a feasibility study should be adequate to estimate the uncertain critical parameters (SD for continuous outcomes; consent rates, event rates, attrition rates for binary outcomes) needed to inform the design of the full RCT with sufficient precision. A sample size of 40 patients allows a standard deviation, for a continuous outcome such as accuracy of radiotherapy (measured in mm), to be estimated to within a precision of approximately ±23% of its true underlying value with 95% confidence. Therefore, allowing for a 20% attrition or loss to follow-up we propose to recruit and randomise 25 patients per group (50 in total). This SD estimate will be synthesised with standard deviations observed in other published studies and on going trials to provide a robust estimate for use in the sample size calculation for the full trial. Preliminary estimates suggest the definitive RCT would need to have between 192 and 266 patients, in total, to detect a standardised effect sizes of between 0.50 to 0.40 at conventional levels of power (90%) and significance (5% two-sided).

For the parameters such as skin reaction measured by RTOG scoring system, a score of 3 or more on the 0 to 4 integer scale would be regarded as a negative event. With 20 randomised patients in the support bra group; then if none of these patients had a RTOG score of 3 or more; then we would be 95% confident that the true negative event rate would lie between 0 and 16.1%. Observing one or more patients with RTOG scores of 3 or more would suggest that the underlying negative event rate for the support bra, is between 1% and 24%, which is not adequate enough for the support bra in its present form to replace existing practice (ie no immobilisation) and requires further development and refinement.

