#### 7.2 Plan acceptability

Patients randomised to receive the intervention (the S4A bra) will have two CT planning scans (one with and one without the S4A bra). Each scan will be planned as normal but patients will only be treated using the plan with the patient wearing the S4A bra. Both scans will be compared using the following parameters:

- Time taken to achieve an acceptable plan
- Beam energy required to achieve an acceptable plan
- Comparison of dose volume histograms for Planning Target Volume (PTV), lungs and heart (for women planned for a left sided breast cancer).
- Dose to organs at risk, lungs and heart mean doses (see section 7.5 for specific dose measurements to be recorded).

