# Table 2 The Research Questions and the associated outcome measures proposed for this feasibility trial.

No	Research question	Proposed Assessment Method
1	Is the design and current functionality of the bra able to fit with current set-up procedures without too much process adaptation?	Interview of staff involved in the planning and treatment of patients using the bra.
2	Does the bra make it easier to produce an acceptable treatment plan?	Those in the intervention arm will undergo two planning CT scans one with and one without the S4A bra. Two radiotherapy treatment plans will be produced for each patient in the intervention arm; the patient will only be treated using the plan with the patient wearing the S4A bra. Plan evaluations will include measures of dose homogeneity across the planning target volume, time taken to plan, complexity of plan and beam energy required to produce the optimal plan.
3	What are the random and systematic errors in breast positioning with the immobilisation support bra compared with a control group with standard immobilisation (no bra)?	Accuracy derived from on-treatment images on days 1-3 and weekly until the end of treatment for five different parameters (see section 12.1).
4	Is accuracy of positioning using the support bra the same across all breast sizes?	Using individual mean random and systematic errors to correlate with breast volume taken from the radiotherapy plan.
5	What are the differences in the dose to organs at risk when the support bra is used compared with no support bra?	Mean lung and mean heart dose compared between bra and no bra cohorts.
6	Does the support bra reduce the	Skin assessments by health care

	incidence of dry/moist desquamation in the inframmary fold	practitioners taken at baseline and weekly during treatment with comments on the skin scoring (using RTOG) in the inframmary fold ie dry/moist desquamation yes/no and duration
7	Is the current inflation bra design appropriate for patients' aesthetic, and comfort needs?	Assessed with comfort assessment tool (using questions derived from Healthy Volunteer study questionnaire analysis and interviews).

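### The lung and heart dose stop/go criteria compare different women across arms, although the more precise with-bra versus without-bra comparison in the same women is already planned and is not tied to them.

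*Protocol*

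**What the plan says.** Two stop/go criteria in Protocol section 3.1, Table 1, concern organ dose. The lung rule fires on "Mean lung dose, no improvement in mean lung doses over control arm". The heart rule fires on "Mean heart dose (left sided cases only), no improvement in mean heart doses over control arm". Both name the control arm as comparator, and neither gives a minimum improvement or an interval. When either fires, inflation levels are reviewed, changes to them are recommended, and the table adds "further experimental testing recommended before definitive RCT".

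Table 2, research question 5, uses the same contrast: "Mean lung and mean heart dose compared between bra and no bra cohorts".

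Section 4.0 describes the two planning scans of each intervention patient as a repeated measures design. Under section 7.2 each scan is planned, and "Both scans will be compared using the following parameters", a list that includes mean lung and mean heart dose. Section 4.0 then describes the purpose as follows: "Thus enabling a direct comparison between participants of dose homogeneity achievable with and without the bra".

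Section 5.2 randomises 25 women per group, after a 20% allowance for attrition on 40 evaluable. Section 6.1 stratifies by bra size only, not by side. Section 7.5 measures organ dose at the planning stage in all patients. Section 17.0 promises a focus on confidence intervals in general, without linking it to the dose criteria.

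**The concern.** Organ dose depends on a woman's anatomy as well as on the bra. A comparison of bra patients with control patients carries the full between-woman variation of both groups. A comparison of two plans for the same woman removes whatever is common to both. The protocol creates the second comparison, at the price of one extra planning CT (7.2 mSv, section 21.0) for each intervention patient, but rests its dose criteria on the first.

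The heart rule is the more exposed. It counts left-sided cases only, their number is not stated, and the randomisation does not balance them.

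At stake is a chance difference in anatomy deciding whether inflation levels are reviewed and further testing is recommended before the definitive trial. A bra that lowers dose could trigger that step, and a bra that does not could avoid it. Section 3.1.1 also reads the accuracy results together with the dose results, so a noisy dose result affects how the main efficacy data are interpreted.

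**Working it through.** **The plan's own figure.** 40 / (1 − 0.20) = 50, or 25 per group. This reproduces section 5.2. The protocol states no error rate for the dose criteria, so there is nothing further to reproduce.

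**Inputs from the protocol.** Lung: up to n = 25 per arm, since dose is recorded at planning, before most attrition can occur. Heart: left-sided cases only, number not given.

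**Inputs assumed.** About 12 left-sided cases per arm (roughly half). Correlation rho between a woman's two plans of 0, 0.5 or 0.8. Equal SD with and without the bra. True reduction d in units of the between-woman SD, from 0 to 0.5. The rule is read on the point estimate, because Table 1 gives nothing else to read it on.

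**Formulas.**
- Between arms: SE = SD × √(2/n)
- Paired, bra arm only: SE = SD × √(2(1 − rho)/n)
- Chance of reading no improvement: Φ(−d/SE), with d and SE both in SD units

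**Standard errors, in SD units.**
- Lung, n = 25: between arms √(2/25) = 0.283; paired at rho 0.5, √(1/25) = 0.200; at rho 0.8, √(0.4/25) = 0.126.
- Heart, n = 12: between arms √(2/12) = 0.408; paired at rho 0.5, √(1/12) = 0.289; at rho 0.8, √(0.4/12) = 0.183.

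At rho 0 the paired formula reduces to √(2/n), the same as between arms.

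**Worked case, lung, d = 0.25.** Between arms Φ(−0.25/0.283) = Φ(−0.88) = 18.8%. Paired at rho 0.5, Φ(−1.25) = 10.6%. At rho 0.8, Φ(−1.98) = 2.4%.

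**Chance of wrongly reading no improvement:**

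| True reduction (SD) | Lung, between arms | Lung, paired 0.5 | Lung, paired 0.8 | Heart, between arms | Heart, paired 0.5 | Heart, paired 0.8 |
|---|---|---|---|---|---|---|
| 0.20 | 24.0% | 15.9% | 5.7% | 31.2% | 24.4% | 13.7% |
| 0.25 | 18.8% | 10.6% | 2.4% | 27.0% | 19.3% | 8.5% |
| 0.40 | 7.9% | 2.3% | 0.1% | 16.4% | 8.3% | 1.4% |
| 0.50 | 3.9% | 0.6% | <0.1% | 11.0% | 4.2% | 0.3% |

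**No true effect.** At d = 0, Φ(0) = 50% in every column. A point-estimate rule reads improvement half the time whether or not the data are paired.

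**Width of the 95% CI, lung, n = 25.** Between arms, 2.011 × 0.283 = ±0.57 SD (48 df). Paired, 2.064 × 0.200 = ±0.41 SD at rho 0.5, and 2.064 × 0.126 = ±0.26 SD at rho 0.8 (24 df).

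**The case against.** The strongest defence is that the paired comparison is not missing. A reader might infer that the protocol exposes women to a second scan and never uses it for organ dose. The documents do not support that: section 7.2 compares the two plans on mean lung and heart dose, section 10.7 records the parameters of each plan, and section 3.1.1 says the data will be viewed together. Section 4.0 also ties the extra scan to plan quality and ease of planning, so a dose criterion on another contrast does not contradict its stated purpose. What stands is narrower: Table 1 and research question 5 name the control arm and so leave the paired result outside the rule.

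A reader might also infer that a fired rule ends the programme or sends the bra back for redesign. Table 1 says neither. It leads to a review and a recommendation, as one of seven criteria.

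The between-arm contrast has real merits. It is the randomised one, it matches a parallel-group definitive trial, and all its plans are used for treatment, whereas the no-bra plan in the bra arm is never delivered. This carries limited weight here, because the control-arm doses are also planning-stage doses (section 7.5). It is still a reason to keep the contrast as support.

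How improvement is judged may be set out in an analysis plan that is not shown, and section 17.0 favours intervals. That tempers any complaint about the missing margin, but not the point about the comparator, which the protocol itself fixes.

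Finally, the size rests on assumptions. At a true 0.5 SD reduction the between-arm lung error is only 3.9%. The phantom result in section 2.1 (mean heart dose 5.1 to 3.7 Gy) cannot be put on this scale, because no between-patient SD is given.

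**Conclusion.** The point holds in a limited form. Both dose criteria rest on a comparison of different women, while a more precise comparison that is already planned is left out of the decision. Under the assumed inputs, and for a true 0.25 SD reduction, pairing lowers the chance of wrongly reading no improvement from about 19% to 11% or 2% for lung, and from 27% to 19% or 9% for heart (rho 0.5 or 0.8). The gain shrinks for larger effects and vanishes at rho 0. A positive correlation is to be expected, since both plans share one woman's anatomy, but its size is unknown.

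It would be tempting to conclude that pairing makes the rule sound. It does not: with no true effect, a paired point estimate still shows improvement half the time, so how the interval is read must also be stated.

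The description of the two-scan comparison in section 4.0 as between participants is a wording slip. The sentence before it calls the design repeated measures, and the comparison is within participants.

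**What to change.** 1. In Table 1 and research question 5, base the mean lung dose and mean heart dose criteria on the paired mean difference (with-bra plan minus without-bra plan) in the intervention arm, with its 95% CI.
2. State how that interval is read against improvement, for example whether it must exclude zero or a named minimum difference. The choice belongs to the trial team.
3. Keep the randomised between-arm difference, with its CI, as supportive. Report the number of left-sided cases behind each heart dose estimate.
4. In section 4.0, change between participants to within participants.

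The data are already collected, so no patients, scans or exposure are added. It is nonetheless a change to a prespecified criterion and needs a protocol amendment. There is a small downside: the lead contrast would no longer be the randomised one and would rest on a no-bra plan that is not delivered, which is why item 3 matters.
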